7.2 Radiographic Progression-Free Survival (PCWG3 / RECIST 1.1)

Radiographic progression-free survival is defined as the interval from the date of randomisation to the date of first evidence of radiographic progression on imaging (PCWG3 criteria for bone lesions, see Appendix 3 and RECIST 1.1 for soft tissue lesions, see Appendix 1), or the date of last known follow-up without progression.

7.3 PSA response rate (PSA RR)

PSA response rate is defined as the proportion of participants in each group with a PSA reduction of $\geq 50\%$ from baseline.

Early rises in PSA prior to 12 weeks will be disregarded in determining PSA response (see Appendix 3 for more details on the PCWG3 criteria).

7.4 Pain response and Progression-Free Survival (PPI)

Pain is measured using the McGill-Melzack Present Pain Intensity scale (PPI, see Appendix 4).

Pain Response is defined as a reduction of 2 or more points for participants with a baseline PPI score of ≥ 2 .

Pain progression is defined as and an increase of 1 or more points in the nadir PPI score.

7.5 Clinical progression-free survival

Clinical progression free survival (PFS) is defined as the interval from the date of randomisation to the date of first clinical evidence of disease progression or death from any cause, whichever occurs first, or the date of last known follow-up without clinical progression.

Clinical progression is defined by progression on imaging (PCWG3 criteria for bone lesions and RECIST 1.1 for soft tissue lesions; see Appendix 1 & 3), development of symptoms attributable to cancer progression, the need for radiotherapy to new metastases or initiation of other anticancer treatment for prostate cancer.

7.6 Aspects of Health related quality of life (HRQL)

Aspects of HRQL will be reported by participants using the EORTC core quality of life questionnaire (QLQ C-30; Appendix 5), the Patient Disease and Treatment Assessment Form (PDF; Appendix 6) and the Fear of Cancer Progression Form (Appendix 7).

The QLQ-C30 is a validated questionnaire developed to assess HRQL in cancer patients. It includes five functional scales (physical, role, cognitive, emotional, and social), three symptom scales (fatigue, pain, and nausea and vomiting), and a global health and quality-of-life scale. The remaining single items assess additional symptoms commonly reported by cancer patients (dyspnoea, appetite loss, sleep disturbance, constipation, and diarrhoea), as well as the perceived financial impact of the disease and treatment. Recent advances in the implementation of the EORTC QLQ-C30 mean that it can now also be used as a source of utility scores, by applying the QLU-C10D algorithm, for use in the construction of quality adjusted life years (QALYs).

Patient DATA Form (Patient Disease and Treatment Assessment Form – 47 items) a simple, multi-item quality of life instrument based on 11-point numeric rating scales for a range of relevant symptoms and functions. It combines cancer specific items from the UBQ-C, GLQ-8 and LASA cancer-specific quality of life instruments.

7.7 Overall Survival (death from any cause)

Overall survival is defined as the interval from date of randomisation to the date of death from any cause, or the date of last known follow-up alive.

7.8 Frequency and Severity of Adverse Events (CTCAE v5.0)

The CTCAE v5.0 will be used to classify and grade the intensity of adverse events during study treatment.

7.9 Associations between Clinical Outcomes and Imaging Analyses at Baseline and During Treatment

Imaging analysis of the translational and standard of care imaging will be undertaken using a variety of methods to develop, validate and compare predictive and prognostic biomarkers for both enzalutamide treatment and enzalutamide and Lu-PSMA therapy. These include but are not limited to analyses of:

- Associations of screening whole body quantitative parameters on ^{68}Ga -PSMA PET/CT and ^{18}F FDG PET/CT will be undertaken. The parameters evaluated will include, but are not limited to SUV max, PSMA-avid tumour volume defined by all disease with SUV greater than 3 for ^{68}Ga -PSMA PET/CT, and SUV mean (total body assessment using all tumour sites with an SUV max > 3 and lesion volume > 2 mL) of these tumour volumes. The prognostic value of the baseline parameters will be explored using PSA and radiographic PFS, and all clinical endpoints.

- Association between the change (difference in SUV max, SUV mean and total tumour volume from baseline to Day 15 or baseline to day 92) on whole body quantitative PET parameters between the baseline and Day 15, Day 92 and at first progression (PSA or radiographic progression, whichever occurs first) will be undertaken. All ⁶⁸Ga-PSMA PET/CT and ¹⁸F FDG PET/CT will be analysed centrally using MIM software technology to evaluate changes in SUV max, total body SUV mean and total tumour volume (total body assessment using all tumour sites with an SUV max > 3 and lesion volume > 2 cm³).
- Using the ⁶⁸Ga-PSMA PET/CT at Day 92, assessment of quantitative whole body PET findings will help determine the proportion of men with persistent PSMA avid disease volume in those undergoing either enzalutamide or enzalutamide and Lu-PSMA treatments. Correlation will be undertaken between absolute reduction in PSA from baseline, RECIST response, PSA and radiographic PFS. Comparison of PSMA quantitative parameters will also be undertaken between the two randomised trial groups to determine if PSMA disease volume is lower in men receiving Lu-PSMA and if this impacts treatment response. Determining proportion of men on enzalutamide alone who have persistent disease volume on ⁶⁸Ga-PSMA PET/CT at Day 92 will inform future combination therapy protocols and trial design.
- A visual scoring system will be assessed for both ⁶⁸Ga-PSMA PET/CT and ¹⁸F FDG PET/CT to evaluate and validate its use in treatment response. The visual scoring assessment will be undertaken by all local sites using a pre-developed model (see Nuclear Medicine Manual). Visual assessment scores will be derived for all PET imaging time points.

The PSMA PET scoring system will use a variation of the PROMISE (47) method whereby a score for intensity and progression is determined for each time point based on the baseline ⁶⁸Ga-PSMA PET/CT scan. This scoring system utilises disease intensity at blood-pool, liver and parotid levels (see Nuclear Medicine Manual). The analysis will evaluate the prognostic and predictive value of a visual scoring system for PSA and radiographic progression. This will be compared to RECIST and PCWG3 reported standard of care bone scan and CT scan undertaken within the trial, to PSA and radiologic PFS in addition to other clinical markers of progression.

The FDG PET scoring system will be a modified Deauville criteria (see Nuclear Medicine Manual). This will be undertaken for the baseline and PSA progression ¹⁸F FDG PET/CT scans. Direct comparison will be made to RECIST and PCWG3 criteria standard of care imaging in determining disease progression.

- QTBI (Quantitative total body imaging) heterogeneity assessment: Taking the MIM total body analysed datasets, analysis of individual tumour sites identified on ⁶⁸Ga-PSMA PET/CT will be undertaken using radiomic quantitation. Individual lesional heterogeneity using complex radiomic techniques will then be compared to both total body quantitation, RECIST, CTC, PSA and radiographic PSA progression.

7.10 Associations between Clinical Outcomes and Possible Prognostic and/or Predictive Biomarkers (tissue and circulating) including CTCs and ctDNA

Translational research will include identifying tissue and circulating biomarkers that are prognostic and/or predictive of response to treatment, safety and resistance to study treatment (associations of biomarkers with clinical outcomes). These include, but are not limited to analyses of:

- i. Liquid biopsies: Liquid biopsies will be collected at molecular imaging time points including at baseline, Day 92 and at first progression.
- ii. CTC: CTCs may be enumerated and analysed at the above time points for a variety of biomarkers including the following:
 - Analysis of androgen receptor splice variants (AR-v7), both enumeration and copy number, and PSMA expression will be utilised at each imaging time point.
 - The CTC platform is capable of evaluating receptor expression heterogeneity and will be able to assess primary resistance and developed resistance to both enzalutamide and combination treatments.
 - As the CTC will be collected as matched pair assessments with PET and ctDNA, there can be correlative evaluation between techniques including evaluating the presence of androgen splice variance and PSMA expression on PSMA PET.
 - Further, CTC biomarkers can be correlated directly to PSA and radiographic progression for prognostic and predictive evaluation. The value of both circulating tumour cells and PET for prognostic purposes and participant treatment selection will be directly compared.
- iii. ctDNA analysis: A mutation profile of key homologous recombination genes will be analysed with PSA response and other clinical outcomes.
- iv. Tissue: archival tissue will be retrieved for translational research. Fresh tissue biopsies may be analysed to assess for patterns of resistance and genomic profiling.

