Randomisation (1:1) to enzalutamide plus Lu-PSMA versus enzalutamide alone. A sample size of 160 participants recruited over 12 months and followed until 150 events have occurred (approximately 18 months extra), would provide 80% power at the two-sided 5% level of significance to detect a HR of 0.625 assuming a median PSA PFS of 5 months in the enzalutamide alone arm, whilst allowing for non-adherence to assigned treatment in up to 2 participants.

[figure not shown]
Study Schema*

Eligibility

Confirmed mCRPC with PSA rising and ≥ 5 ng/mL
No chemotherapy for mCRPC
 ≥ 2 high risk features for early failure on enzalutamide
Baseline PSMA SUV max > 15 on ^{68}Ga -PSMA PET/CT

Stratification

Study site
Volume of disease (> 20 vs ≤ 20 sites)
Early docetaxel for castration-sensitive disease (Y/N)
Prior treatment with abiraterone (Y/N)

* Refer to section 6.2.3 for translational research components schema

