3 DESIGN

Randomised, phase 2, stratified, multicentre, open label clinical trial.

Participants will be randomised to enzalutamide or enzalutamide and Lu-PSMA in a 1:1 ratio. A minimisation approach will be used to minimise chance imbalances across the following stratification factors: study site, volume of disease (>20 versus ≤ 20 sites of disease measured on ^{68}Ga -PSMA PET/CT), prior treatment with early docetaxel for castration-sensitive disease (yes vs no), and prior treatment with abiraterone (yes vs no).

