13 STATISTICAL CONSIDERATIONS

13.1 Sample Size

The study will randomise patients to the experimental combination of enzalutamide and Lu-PSMA versus enzalutamide alone in a 1:1 ratio. A sample size of 160 patients recruited over 12 months and followed until 150 events occurred (approximately another 18 months), provides 80% power at the two-sided 5% level of significance to detect a HR of 0.625 assuming a median PSA PFS of 5 months in the enzalutamide alone arm whilst allowing for non-adherence to assigned treatment in up to 2 participants.

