16.3 Appendix 3: Prostate Cancer Working Group 3 (PCWG3) Criteria

The sections that apply to this trial are the criteria for PSA response and progression, and the criteria for bone lesion “prevent/delay end points (progression).

Variable	PCWG3 (2016)
PSA	
 - Recognize that a favorable effect on PSA may be delayed for 12 weeks or more, even for a cytotoxic drug - Monitor PSA by cycle but plan to continue through early rises for a minimum of 12 weeks unless other evidence of progression - Ignore early rises (prior to 12 weeks) in determining PSA response 
For control/relieve/eliminate endpoints:
 
 - Describe absolute changes in PSA over time from baseline to best response 
For delay/prevent endpoints:
 
Decline from baseline:
 
 - Record time from start of therapy to first PSA increase that is $\geq 25\%$ and ≥ 2 ng/mL above the nadir, and which is confirmed by a second value 3 or more weeks later (ie, a confirmed rising trend) 
No decline from baseline:
 
 - PSA progression $\geq 25\%$ and ≥ 2 ng/mL after 12 weeks

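### The Day 92 PET analysis in Section 7.9 uses the absolute PSA fall, which scales with baseline PSA, so its correlation with residual PSMA disease is weakened and, under some assumptions, lost or reversed (minor)

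*Protocol*

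**What the plan says.** The third bullet of Section 7.9 starts from the Day 92 PSMA PET scan: "assessment of quantitative whole body PET findings will help determine the proportion of men with persistent PSMA avid disease volume". Its next sentence reads: "Correlation will be undertaken between absolute reduction in PSA from baseline, RECIST response, PSA and radiographic PFS". That sentence gives no unit for the PSA fall and does not name the imaging variable. The bullet then compares PSMA parameters between the randomised groups.

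The section introduces its list of analyses with "These include but are not limited to analyses of", and the biomarker objective it serves (objective 10, Section 2) is tertiary.

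Three other places bear on the choice of scale:
- Section 7.3: "PSA response rate is defined as the proportion of participants in each group with a PSA reduction of" at least 50% from baseline, which is a relative measure.
- The eligibility box of the study schema: "Confirmed mCRPC with PSA rising and" at least 5 ng/mL. Inclusion criterion 3 in Section 4.2 sets the same floor, and neither sets a ceiling.
- Appendix 3, for one class of endpoints: "Describe absolute changes in PSA over time from baseline to best response". This asks for description and does not mention a correlation with imaging.

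**The concern.** A fall in ng/mL depends on how far PSA fell and on where it started. A man who starts at 10 and falls by 90% drops 9 ng/mL. A man who starts at 500 and falls by 30% drops 150 ng/mL. Section 7.3 counts the first as a responder and the second as a non-responder, yet the absolute scale ranks the second far higher.

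PSMA-avid volume at Day 92 likewise depends on the volume at the start. If men with high PSA also tend to have high volume, the starting burden pushes both variables up together. That positive component works against the negative association one would expect if residual disease marks a poorer response.

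At stake is one exploratory imaging-outcome association. A correlation near zero, or with the wrong sign, could be read as evidence against Day 92 PSMA volume as a marker when it came from the choice of scale.

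**Working it through.** Section 7.9 gives no figure to reproduce, and the sample-size calculation in Section 13.1 does not enter.

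**Structure.** Let P0 and P1 be PSA at baseline and later, V0 and V1 PSMA-avid volume at baseline and Day 92, and R = P1/P0, S = V1/V0.
- Absolute fall: P0 - P1 = P0 × (1 - R). When PSA falls, this is less than P0 and proportional to it.
- Percentage fall: 1 - R, which does not contain P0.
- Residual volume: V1 = V0 × S.

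The correlation of P0 × (1 - R) with V0 × S therefore mixes the baseline link (P0 with V0) and the response link (R with S).

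**Check by arithmetic.** 10 × 0.90 = 9 ng/mL; 500 × 0.30 = 150 ng/mL.

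**Size, by simulation.** Every input here is an assumption, because the documents give none of them:
- baseline PSA and volume log-normal with equal log-SD of 0.5, 0.8, 1.0 or 1.3;
- log-scale baseline correlation rho of 0, 0.3, 0.5 or 0.7;
- SD of log-response 0.5 (modest) or 1.0 (wide);
- correlation between PSA response and volume response 0.7 on the log scale;
- median falls of 75% (PSA) and 50% (volume);
- 60,000 men per scenario, one group, entry floor of 5 ng/mL not imposed.

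This gives 4 × 4 × 2 = 32 scenarios. Spearman correlation of Day 92 volume with PSA fall, as a range over the four baseline log-SDs:

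| rho | Response SD | Absolute fall | Percentage fall | Wrong sign, absolute |
|---|---|---|---|---|
| 0 | 0.5 | -0.18 to -0.04 | -0.47 to -0.24 | 0 of 4 |
| 0 | 1.0 | -0.39 to -0.20 | -0.61 to -0.41 | 0 of 4 |
| 0.3 | 0.5 | 0.00 to +0.23 | -0.48 to -0.24 | 3 of 4 |
| 0.3 | 1.0 | -0.30 to -0.01 | -0.61 to -0.41 | 0 of 4 |
| 0.5 | 0.5 | +0.13 to +0.40 | -0.48 to -0.24 | 4 of 4 |
| 0.5 | 1.0 | -0.25 to +0.11 | -0.61 to -0.42 | 2 of 4 |
| 0.7 | 0.5 | +0.25 to +0.57 | -0.48 to -0.25 | 4 of 4 |
| 0.7 | 1.0 | -0.19 to +0.22 | -0.61 to -0.41 | 3 of 4 |

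Wrong sign in total: 3 + 4 + 2 + 4 + 3 = 16 of 32 on the absolute scale, and 0 of 32 on the percentage scale.

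Further results:
- Absolute fall correlates 0.65 to 0.97 with baseline PSA across the 32 scenarios.
- With no baseline spread (log-SD 0) the two scales agree, at -0.68 to -0.69.
- If the imaging term is percentage fall in volume, the sign holds, but the correlation with PSA fall is 0.11 to 0.44 on the absolute scale against 0.68 to 0.69 on the percentage scale.
- With Pearson in place of Spearman, the absolute scale has the wrong sign in 12 of 32 scenarios.

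Even with percentage PSA fall, the correlation with raw Day 92 volume shrinks from -0.68 to as little as -0.24 as baseline spread grows, because V1 still carries V0. That is why the fix includes baseline volume.

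**The case against.** The sentence names no unit and no imaging term. The PET variable could be a yes/no status for persistent disease, a percentage change in volume or another parameter, and the sentence could even be read as correlating the listed outcomes with one another. This stands: residual volume and ng/mL are the natural reading of the bullet, not its text. The unnamed term is itself worth correcting.

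The correlation method and any baseline adjustment are ordinary content for a statistical analysis plan, which Section 13.2 announces, and the list in Section 7.9 is open-ended. This also stands, so the absence of an adjustment is not held against the protocol. The PSA scale is different, because the protocol itself fixes it.

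The consequence is small. The same sentence also uses RECIST response, PSA PFS and radiographic PFS, and the between-group comparison of PSMA parameters does not depend on the PSA scale. This stands and sets the weight of the point.

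A reader might infer three stronger claims that the documents do not support:
- That the protocol otherwise measures PSA change only relative to baseline. Section 7.1 defines progression from the nadir and adds a 2 ng/mL minimum to the 25% rise, and Appendix 3 asks for absolute changes to be described. The contrast is with Section 7.3.
- That the absolute fall mainly measures tumour burden. The 0.65 to 0.97 found above is with baseline PSA, under assumed spread. How closely PSA tracks burden in these men is not stated.
- That the association will disappear or reverse. That needs a baseline PSA-volume correlation that the documents do not give.

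**Conclusion.** The point holds as a minor one. Section 7.9 fixes a PSA measure that is bounded by baseline PSA and scales with it, in a population with a PSA floor and no ceiling, so baseline burden partly drives the correlation.

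Given any of the baseline spreads assumed here, the association is attenuated under either volume reading of the imaging term. Loss or reversal of sign is conditional: it needs residual volume as the imaging term and a baseline PSA-volume correlation of about 0.3 or more with modest response spread, or 0.5 to 0.7 with wide response spread and large enough baseline spread. At zero baseline correlation the sign never changed.

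The effect is confined to one tertiary, exploratory correlation. The primary endpoint, the PSA response rate, the sample size and the other correlates in the sentence are unaffected.

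**What to change.** In the Day 92 bullet of Section 7.9:
- name both terms of the correlation, including which Day 92 PSMA parameter is meant;
- use percentage or log-ratio change in PSA from baseline as the PSA term;
- adjust the association for baseline PSA and baseline PSMA volume (here or in the statistical analysis plan);
- keep absolute PSA change as a description only, as in Appendix 3.

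The cost is a change of wording. Baseline PSA, on-treatment PSA and the screening and Day 92 PSMA scans are already collected, so no data, visits or participants are added.

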13.2.1 Analysis of Health Outcomes Relative to Costs

The incremental cost will be estimated by applying unit costs to the resource usage data. Hospital-specific costs (e.g. AR-DRG cost-weights) and market prices are likely to be available for most of the resource items (e.g. MBS-fees and PBS prices). This will include estimates for the time and resource use associated with the delivery of Lu-PSMA. In the absence of market prices, data from the literature and expert opinion will be used to estimate the costs associated with the relevant resources used. Cost comparisons will be presented by health care type used, cost per unit of health care (eg PBS price) and total cost of health care used over the period of the trial. Mean estimates of costs will be used and confidence intervals generated by boot-strapping the data.

Results for the cost-effectiveness analysis will be presented as the cost per QALY gained for the addition of Lu-PSMA to enzalutamide versus enzalutamide alone. The robustness and validity of the results will be explored using sensitivity analyses by varying the parameter inputs. As the proportion of patients alive at the end of the study is likely to be sufficiently large, the longer-term comparative effects of Lu-PSMA plus enzalutamide compared with enzalutamide will be investigated by extrapolating the outcomes (QALYs) and costs associated with the two approaches to the treatment.

Importantly, the modelled analysis will consider the results from the trial with respect to the ability to predict which patients are most likely to benefit from treatment with Lu-PSMA therapy, since the ability to target therapy to those most likely to benefit will have important implications for patient outcomes and cost-effectiveness. This will use data from the trial, extrapolated using data from existing studies, to model what might be expected over the lifetime of prostate cancer patients, allowing for the potential to incorporate more targeted patient selection strategies.

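### Sections 7.9 and 7.10 offer association with progression as evidence of predictive value, which tests prognosis only, so a purely prognostic marker could be reported as predictive of Lu-PSMA benefit

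*Protocol*

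**What the plan says.** The protocol's aim (section 2) includes finding potential prognostic and predictive biomarkers; the work falls under a tertiary objective.

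- Section 7.10, CTC item: "CTC biomarkers can be correlated directly to PSA and radiographic progression for prognostic and predictive evaluation". The next sentence says that CTCs and PET will be compared directly for prognosis and for selecting participants' treatment.
- Section 7.10, opening sentence: prognostic and predictive markers are introduced together and explained in brackets as associations of markers with clinical outcomes.
- Section 7.9, visual PET score: "The analysis will evaluate the prognostic and predictive value of a visual scoring system for PSA and radiographic progression".
- Section 7.9, opening: imaging is to be used to "develop, validate and compare predictive and prognostic biomarkers for both enzalutamide treatment and enzalutamide and Lu-PSMA therapy".
- Section 13.2 describes no biomarker analysis. The only interaction it names is time point by treatment in the quality-of-life mixed model.
- Section 13.2.1: the cost-effectiveness model will consider the trial's results on "the ability to predict which patients are most likely to benefit from treatment with Lu-PSMA therapy".

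Two items are worded more narrowly. Baseline quantitative PET parameters are given prognostic value only (section 7.9). The ctDNA item makes no predictive statement of its own; only the general sentence of 7.10 reaches it.

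**The concern.** A prognostic marker separates men with good and poor outcomes whatever they receive. A predictive marker separates men for whom adding Lu-PSMA helps more from those for whom it helps less. The null hypotheses differ: no relation between marker and outcome in the first case, the same treatment effect at every marker level in the second. Correlation with progression addresses only the first.

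The protocol uses the word predictive in the second sense. Section 1.2 calls AR-V7 prognostic at best while no alternative strategy is proven. Section 1.9 wants CTCs to find men who will not respond to single-agent AR-directed therapy but may respond to the combination. The sentence after the CTC quote concerns treatment selection. So this is more than detail left for the SAP: a method is named, and it answers a different question.

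At stake is the reading of the translational results. Markers of aggressive disease could be reported as identifying men who benefit from Lu-PSMA. Conversely, a marker whose effects run in opposite directions in the two arms could show little overall association and be missed.

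**Working it through.** **Inputs from section 13.1.** The design "provides 80% power at the two-sided 5% level of significance to detect a HR of 0.625". Other inputs: 160 men accrued over 12 months; analysis at 150 events; control-arm median of 5 months; 1:1 allocation; up to 2 non-adherent participants.

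**Assumed, not in the protocol.** Marker prevalence p of 20%, 30% or 50%; prognostic hazard ratio (HR) of 1.5, 2.0 or 2.5, identical in both arms. A ratio of HRs of 0.5 is used to size the interaction test.

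**1. The plan's own figure.** With (1.960 + 0.842)² = 7.849:
- Schoenfeld: 7.849 / (0.25 × (ln 0.625)²) = 7.849 / (0.25 × 0.2209), giving 143 events.
- Freedman: 7.849 × (1.625 / 0.375)², giving 148 events.
- Schoenfeld with the log HR diluted by 2/80: HR 0.625^0.975 = 0.632, giving 150 events.

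The stated 150 reproduces. It sizes the treatment comparison; the protocol gives no figure for the biomarker analyses.

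**2. Chance that a purely prognostic marker shows a significant pooled association.** Power = Φ(√(d·p·(1−p)) × |ln HR| − 1.960), with d = 150. For p = 0.30 and HR 2.0: √31.5 × 0.693 = 3.890; 3.890 − 1.960 = 1.930; Φ = 0.973.

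| Prevalence | HR 1.5 | HR 2.0 | HR 2.5 |
|---|---|---|---|
| 20% | 51% | 92% | 99% |
| 30% | 62% | 97% | 99.9% |
| 50% | 70% | 99% | about 100% |

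**3. Simulation of the same marker against the interaction test.** 160 men, 12 months' accrual plus 18 months' follow-up, treatment HR 0.625 in both marker groups (so no predictive effect), prognostic HR 2.0, 600 trials per row, about 144 events on average. Percentage significant at two-sided 5%:

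| Prevalence | Pooled association | Association within combination arm | Treatment-by-marker term |
|---|---|---|---|
| 20% | 92% | 69% | 4.5% |
| 30% | 97% | 79% | 4.3% |
| 50% | 99% | 84% | 6.5% |

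With 600 trials the standard error at a true 5% is √(0.05 × 0.95 / 600) = 0.9 percentage points, so the last column agrees with 5%.

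**4. Price of the right test.** The variance of the log ratio of HRs is 1 / (d·p·(1−p)·¼). For p = 0.30: 1 / (150 × 0.21 × 0.25) = 1 / 7.875, standard error 0.356. For a ratio of 0.5: 0.693 / 0.356 = 1.945; Φ(1.945 − 1.960) = 49%. At 20% and 50% prevalence the power is 40% and 56%. Reaching 80% would need 409, 312 and 262 events at the three prevalences.

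**The case against.** The case against is that no test is fixed. The CTC wording is permissive, the list is open, the text sits among the outcome definitions rather than in section 13, and nothing says when a marker will be called predictive. The SAP or a translational plan could add an interaction model. Much of this stands: the protocol does not bind anyone to report prognostic markers as predictive, and a reader who infers that they would be goes beyond the text. What remains is that the one method named for predictive evaluation cannot deliver it, and an SAP that merely elaborated it would inherit the fault.

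Other stronger readings also fail:

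- **That every marker is affected.** The wording is explicit for CTCs. It is similar for the visual PET score, though that sentence can also be read as forecasting progression. Baseline quantitative PET is prognostic only, and ctDNA is reached only through the general sentence.
- **That 97% is a false-positive rate.** It is the power to detect a real prognostic effect, and becomes an error rate only if the result is read as predictive. Nor does the protocol say that arms will be pooled.
- **That the randomisation is ignored.** Section 7.9 plans markers for both treatments and compares PSMA parameters between groups. No treatment effect is compared across marker levels, however, and association within the combination arm alone does not cure the problem (69% to 84% in step 3).
- **That on-treatment values are useless.** Day 92 PET informs doses 3 and 4, and Day 15 PSMA up-regulation is a named tertiary interest. A Day 15 scan made before the first Lu-PSMA dose is a legitimate candidate marker.
- **That correlation results will drive the cost-effectiveness model.** Section 13.2.1 does not say which estimates it will use; the link is an inference.

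**Conclusion.** The point holds in a limited form. Section 7.10, with similar wording in 7.9, names association with progression as a means of predictive evaluation. That tests prognosis, so a purely prognostic marker could be reported as predictive of Lu-PSMA benefit, although the trial's randomised control arm allows the right contrast.

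At 30% prevalence, prognostic HR 2.0 and 150 events, a marker with no predictive effect shows a significant pooled association in about 97% of trials, against about 5% for an interaction test. Prevalence and marker HR are assumptions; across the range examined the pooled figure runs from 51% to about 100%. The interaction test has modest power here, which is a reason to call its results exploratory and no reason to substitute a test of another hypothesis. The objective is tertiary, and the primary analysis and sample size are unaffected. The change is worth making because it costs little and governs how the translational results are read.

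**What to change.** In sections 7.9 and 7.10, or in the SAP with a matching clarification of the CTC sentence:

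1. Keep correlation with progression for prognostic evaluation only.
2. Judge predictive value with markers measured before the first Lu-PSMA dose: baseline CTC and ctDNA, and screening PET. Use the Day 15 PSMA PET only if scanned before that dose and analysed in both arms from that time point. The order is not guaranteed, since the dose window is ±7 days and the scan window −5/+7 days.
3. Fit a treatment-by-marker term in the Cox model for PSA PFS and radiographic PFS (a logistic model for PSA response), with the clinical stratification factors. Report the Lu-PSMA effect with its 95% CI by marker level.
4. Label these results exploratory.
5. Use Day 92 and progression samples to describe response and resistance.
6. Base any targeted-selection modelling under 13.2.1 on the interaction-based estimates.

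The cost is a few sentences. The samples and scans are already scheduled. The drawback is imprecision: fewer markers will be called predictive.
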